8.1.2 Serious Adverse Events

A serious adverse event (SAE) or reaction is any untoward occurrence that at any dose:

- Results in death,
- Is life-threatening,
- Requires inpatient hospitalization or prolongation of existing hospitalization,
- Results in persistent or in significant disability/incapacity,
- Is a congenital abnormality or a birth defect.

The term "life-threatening" in the definition of "serious" refers to an event in which the participant was at risk of death at the time of the event; it does not refer to an event which hypothetically might have caused death if it were more severe.

8.1.3 Unexpected Adverse Event

An unexpected adverse event is any AE that is not identified in nature, severity or frequency in the current Investigator's Brochure or Product Monograph.

8.1.4 Unexpected Adverse Drug Reaction (ADR)

An ADR is an adverse reaction, the severity of which is not consistent with the applicable Investigator's Brochure or Product Monograph. All noxious and unintended responses to a medicinal product related to any dose should be considered an ADR.

The phrase "responses to a medicinal product" means that a causal relationship between a medicinal product and an adverse event is at least a reasonable possibility, i.e., the relationship cannot be ruled out.

The expression "causal relationship" is meant to convey that in general there are facts, evidence or arguments to suggest a reasonable causal relationship. All serious and unexpected ADRs

will have expedited reporting to regulatory agencies following ICH-GCP and local regulatory requirements.

8.2 Assessment of an Adverse Event

8.2.1 Relationship (Causality/Relatedness)

The causality assessment is the determination, according to the investigator's clinical judgment, of the existence of a reasonable possibility that the study drug (IP) caused or contributed to an adverse event.

If the investigator or delegated sub-investigator is unsure about whether or not the study drug caused or is related to the event, then the event will be handled as "related" to the study drug for reporting purposes of the trial. If the causality assessment is "unknown but not related" to the study drug, this should be clearly documented in the source documents.

8.2.2 Expectedness

Events are classified as unforeseen or unexpected if the nature, severity or frequency is not consistent with the risk information set out in the Product Monograph (PM) or label.

8.2.3 Seriousness

Events are classified as serious if associated with effects threatening the life or physiological functions of a participant. Refer to the definition for "Serious Adverse Events" in section 8.1.2.

8.2.4 Severity

The term "severe" is often used to describe the intensity (severity) of a specific event (e.g. mild, moderate, or severe myocardial infarction); the event itself, however, may be of relatively minor medical significance (such as severe headache). This is not the same as "serious," which is based on participant/event outcome or action criteria usually associated with events that pose a threat to a participant's life or functioning. The terms "serious" and "severe" are not synonymous. Seriousness (not severity) serves as a guide for defining regulatory reporting obligations.

8.3 Adverse Event Recording

Investigations into potential adverse events should be done during each contact with a participant. Investigations may be done through specific questioning and, as appropriate, by examination. Information on all adverse events should be recorded promptly in the source document, and assessed by an investigator in a timely manner allowing sufficient time to meet required reporting timelines for SAEs and SUADRs if needed. Adverse event CRFs should be completed using source documents by a delegated research team member in a timely manner/within 15 days of site awareness. All clearly related signs, symptoms, and abnormal diagnostic procedures should be recorded in the source document, though should be grouped under one diagnosis.

The following are not considered AEs and therefore do not require recording:

- Pre-existing diseases or conditions identified and recorded at screening/baseline unless, at the discretion of the investigator, the disease or condition worsens in severity or frequency
- At the discretion of the investigator, events considered likely manifestations of the underlying disease or that commonly occur in the study population independent of IP exposure
- Elective medical or surgical procedures.

8.4 Reporting of SAEs and Unanticipated Events

8.4.1 Investigator reporting: Notifying the REB

Serious adverse events and unanticipated events should be recorded and reported to the REB in accordance with local reporting requirements and timelines.

8.4.2 Investigator reporting: Notifying the Sponsor

The investigator is responsible for reporting serious adverse events and serious and unexpected adverse drug reactions (SUADRs) to the sponsor in accordance with applicable regulations and reporting requirements and timelines.

Events that are assessed to be **serious and unexpected and related or cannot be ruled out as related** to the investigational product are considered SUADRs. Reporting for SUADRs should include a description of the event in sufficient detail to allow for a complete medical assessment of the case and independent determination of possible causality. The minimum information required includes at least one identifiable participant, one identifiable reporter, one serious reaction, and one suspect product.

Additionally, a Suspect Adverse Reaction Report – CIOMS I Form must be completed by the investigator and forwarded to the Sponsor within 24 hours of site awareness. Information on other possible causes of the event, such as concomitant medications and illnesses should also be provided as soon as is made available.

8.4.3 Sponsor Reporting of SUADRs: Notifying Health Canada

The regulatory sponsor is responsible for reporting serious adverse events and SUADRs to regulatory authorities in accordance with local expedited reporting requirements and timelines. In addition, the Sponsor will complete the ADR Expedited Reporting Summary Form and submit this form in conjunction with the completed CIOMS Form to the appropriate Health Canada directorate.

8.5 Type and Duration of Follow-up for Adverse Events

AEs occurring as of the first administered dose of the investigational product and for a follow up period of 120 minutes after the last administered dose, will be collected. AEs recorded during

this period will be followed through to resolution, or until the event is assessed as chronic or stable.

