2.3 Potential Risks/Benefits and Rationale

The participant population consists of 28 pregnant women between 24-32 weeks' gestation who have screened positive for gestational diabetes on the 50g glucose challenge test. The main drawback to participation is that women will have to undergo two fasting, 1 hour and 2 hour glucose values within one week. Risks involved with participating in the study include: possibility of pain, bruising, swelling or infection related to drawing blood, allergic reaction symptoms such as itching, facial swelling and anaphylaxis upon consumption if the participant has an allergy to corn based products such as dextrose. These risks will be minimized by screening patients for dextrose allergy before having them sign the informed consent form.

The benefit may not be directly to the patient as they will still need to complete the standard 75g glucose beverage test but they will be contributing to new knowledge on alternatives to the standard test that may benefit other pregnant women, including themselves, in the future.

The ultimate goal of this project is to improve women's health by 1) allowing more women to be screened for GDM and 2) providing an equivalent glucose beverage alternative with fewer side effects, making the screening process more comfortable for patients who cannot tolerate

glucose beverage. Improving the tolerability of the test is important because there is growing evidence that GDM significantly increases the risk of short and long term adverse consequences for both the fetus and the mother (10,11). Accurate diagnosis may allow women to implement preventative measures such as healthy lifestyle, which has shown to be effective in preventing T2DM in women with previous GDM (19,20). There have been recent quality control issues with the commercially available glucose beverage product (16), so this alternative test could become the standard test if the dose calibration is found to be more reliable.

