6 INTERVENTIONS

6.1 Investigational Product

The investigational product is 4g dextrose monohydrate tablets from Dex4®. They will be used as an alternative carbohydrate source to glucose beverage in 2-hr OGTT testing in this trial.

6.1.1 *Acquisition, Formulation and Packaging*

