6.1.4.3 Dispensing of Investigational Product

21 tablets will be dispensed to each participant; After the fasting blood glucose is drawn they will be instructed to consume the tablets and no more than 300ml of water within 5 min.

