6.2.1 Administration of Intervention

Participants will be asked to ingest 21 Dex4® tablets and no more than 300ml of water within 5 minutes. Blood draws will be performed at fasting (before ingesting the dextrose monohydrate tablets), as well as 1 hour after (+/- 15 minutes) and 2 hours (+/- 15 minutes) after ingesting the dextrose monohydrate tablets.

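### The adverse-event window in Section 8.5 can close before the last permitted blood draw, is too short for a venipuncture infection to appear, and leaves out the beverage test

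*Protocol*

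**What the plan says.** Section 8.5 of the protocol opens AE collection when the first tablet is taken. It sets the end in these words: "for a follow up period of 120 minutes after the last administered dose, will be collected". Events recorded in that period are followed until they resolve or are judged chronic or stable. Section 6.1 identifies the product: "The investigational product is 4g dextrose monohydrate tablets from Dex4". The glucose beverage is the comparator.

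The sampling schedule is set elsewhere. Section 6.1.4.3 puts the first draw ahead of the tablets: "After the fasting blood glucose is drawn they will be instructed to consume the tablets", with 5 minutes allowed for ingestion. Section 6.2.1 places the last draw at "2 hours (+/- 15 minutes) after ingesting the dextrose monohydrate tablets". Section 6.1.3 gives three venipunctures per test, so six over the two tests.

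Section 2.3 lists among the study risks the "possibility of pain, bruising, swelling or infection related to drawing blood".

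**The concern.** A collection window should at least contain the study procedures it is meant to monitor and leave time for the harms the protocol names. This window was set from tablet ingestion alone, without reference to the draw tolerance in Section 6.2.1 or the venipuncture risks in Section 2.3. It also follows one product only, although Sections 3.2 and 10.1 ask whether the tablets cause fewer side effects than the beverage.

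What is at stake is how the safety section of the report can be read. If Section 8.5 is followed as written, a statement that no blood-draw infections occurred would say little, because collection ended before one could show. A count of AEs under Section 8.5 would also describe the tablet test and not the beverage test, so it could not be set beside a beverage count.

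**Working it through.** The 120 minutes is a stated rule, not a derived figure, so there is no calculation to reproduce. The check compares the protocol's own times.

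**Inputs**
- Window opens at the first tablet (Section 8.5).
- Window closes 120 minutes after the last tablet (Section 8.5).
- Ingestion takes up to 5 minutes (Sections 6.1.4.3 and 6.2.1).
- The fasting draw precedes the first tablet (same sections).
- The final draw is due at 120 ± 15 minutes, that is 105 to 135 minutes after ingestion (Section 6.2.1).

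Section 6.2.1 does not say whether draw times run from the start or the end of ingestion, so both readings are worked.

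**1. Latest permitted final draw against closure**
- Clock from the end of ingestion: closure at 120; latest draw at 135; gap = 135 − 120 = 15 minutes.
- Clock from the start of ingestion, last tablet at 5 minutes: closure at 5 + 120 = 125; latest draw at 135; gap = 135 − 125 = 10 minutes.

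On either reading a compliant draw can come after closure.

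**2. Earliest permitted final draw against closure**
- Clock from the end: 120 − 105 = 15 minutes of collection left.
- Clock from the start: 125 − 105 = 20 minutes left.

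So after the last venipuncture the window offers between nothing and 15 to 20 minutes.

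**3. Time for an infection to appear**

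The whole window is at most 5 + 120 = 125 minutes long. Even for the fasting draw, the earliest of the three, collection ends about two hours later. The protocol gives no onset time for infection. That one would not be expected to show so soon is a clinical inference, but a safe one.

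**4. The two tests**

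Taking the tests to be on separate days, each after its own fast of at least 8 hours:
- Beverage first: the beverage test is over before the window opens.
- Tablets first: the window has closed before the beverage test starts.

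In neither order is the beverage test inside it.

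**5. Other provisions that might fill the gap**
- Section 8.3 requires AE enquiry at each contact. It does not change the onset limits in Section 8.5.
- Section 8.6 sets reporting clocks for serious events from the time the site becomes aware. It creates no contact through which the site would become aware.
- Section 4.1: Questionnaire A is completed after the first test. Questionnaire B asks about side effects of the second test and preference, not about the days between.
- Section 7.2 describes a screening appointment and two test visits, with nothing after the second test.

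**6. Minimum consistent window**

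To contain every draw of the tablet visit, collection would have to start no later than the fasting draw and run to at least 135 minutes after ingestion, against 120 stated. No length for later events can be derived from the document.

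**The case against.** The strongest defence is that little is lost. Exposure is one dose of 21 tablets. Starting collection at first dose is common and fits the AE definition in Section 8.1.1, which concerns a person given a product. The side-effect outcome comes from the questionnaires, which cover both tests, include an "other" category and state no time cut-off. A woman given tablets first is asked about AEs again within a week under Section 8.3. Serious events that the site learns of are reportable under Section 8.6 whatever their cause, with no onset limit. All of this stands and keeps the point minor. It does not change what Section 8.5 collects, and it gives a woman who takes the tablets second no later contact.

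A reader might also infer more than the text supports:
- *That a known share of final draws is uncovered.* The late part is 15/30 of the permitted range on one clock and 10/30 on the other. Turning either into a share of draws needs an assumed spread of draw times that the protocol does not give.
- *That only the 1-hour draw is properly followed.* Section 8.5 filters on when the event occurs, not on when the needle went in. A bruise from the fasting draw that appears after ingestion starts is collected; only a reaction before the first tablet is missed.
- *That the protocol itself names delayed risks.* Section 2.3 calls no risk delayed and ties allergy to consumption. Diarrhea and abdominal pain are listed in Section 2.1 for the beverage, not for the tablets.
- *That late serious events would go unseen or the stopping rule would be starved.* Section 8.6 covers serious events known to the site. Section 10.3 also allows stopping for new information or other situations.
- *That birth defects are missed through this window.* Section 8.1.2 is a generic definition of seriousness, and no modest extension would reach that outcome.

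**Conclusion.** The point holds as a minor inconsistency with a cheap remedy. A compliant final draw can fall up to 10 to 15 minutes after AE collection closes, depending on which end of ingestion starts the clock. This needs no assumption beyond the two clock readings. Venipuncture infection, a named risk, cannot reasonably be expected inside a window of about two hours; this rests on clinical inference rather than on a stated onset time. The beverage test lies outside the window because Section 6.1 defines the investigational product as the tablets. If that term were read to include the beverage, the days between the tests would be covered, but Section 6.1 does not say so, and events arising after the second test would still be missed.

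The primary glucose comparison and the questionnaire-based side-effect outcome are not affected. What is weakened is the meaning of a low or zero AE count.

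**What to change.** Reconcile Sections 2.3, 6.2.1, 8.3 and 8.5:

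- In Section 8.5, start AE collection at the fasting draw and run it beyond the last permitted draw (135 minutes after ingestion), with the same window after both products.
- Add one item to Questionnaire B asking about any event since the first test, including at the blood-draw sites.
- State a closing point after the second test and how events up to then will be learned of, for example by participant report to the study team. The protocol gives no basis for a particular length, so the sponsor should choose and justify it.
- State in Section 6.2.1 whether draw times run from the start or the end of ingestion.

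The cost is amendment wording, one questionnaire item and a simple route for reports after the second test. The downside is that a few unrelated events will be recorded.

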8.6 Reporting and Entry Timelines

Study investigators will report SAEs to the sponsor within the following timelines:

- All deaths and immediately life-threatening events, whether related or unrelated, will be recorded and reported to the sponsor within 24 hours of site awareness.
- Serious adverse events other than death and immediately life-threatening events, regardless of relationship, will be reported to the sponsor within 72 hours of site awareness.

Adverse event information will be entered into the CRF in a timely manner and **no later than 15 days** from the time the investigator becomes aware of the event.

9 SITE MONITORING, AUDITING AND INSPECTING

9.1 Site Monitoring Plan

Site monitoring is conducted to ensure the safety of human study participants and the protection of their rights and well-being. Monitoring also verifies that collected study data is accurate, complete and verifiable by source documentation and that the study is conducted in accordance with the protocol and operating procedures.

Monitoring for this study is the responsibility of the sponsor. The delegated monitor will evaluate study processes and documentation based on the approved protocol/amendment(s), Part C, Division 5 of the Food and Drug Regulations, the International Conference on Harmonisation (ICH), E6: Good Clinical Practice guidelines (GCP) and institutional policies.

The extent and nature of monitoring is outlined in the Monitoring Plan. The monitoring plan specifies the frequency of monitoring, monitoring procedures, the level of site monitoring activities (e.g., the percentage of participant data to be reviewed), and the distribution of monitoring reports. Monitoring activities will be performed both in person and remotely. Reports of findings identified during monitoring activities will be provided to sites detailing any required actions. Documentation of monitoring activities and findings will be provided to the site study team and the study QI. The institution and/or local REB reserve the right to conduct independent audits as necessary.

The Investigator is responsible for ensuring monitors and/or quality assurance reviewers are given access to all study-related documents noted above and study related facilities (e.g. pharmacy, diagnostic laboratory, etc.), and have adequate space to conduct the monitoring visit or audit.

9.2 Auditing and Inspecting

The investigator will provide direct access to source data/documents for the purposes of study-related monitoring, audits, and inspections by the REB, the sponsor, and applicable regulatory bodies. The investigator will permit the review of all study related documents (e.g. source documents, regulatory documents, data collection instruments, study data etc.) and will ensure access to applicable study-related facilities (e.g. pharmacy, diagnostic laboratory, etc.).

10 STATISTICAL CONSIDERATIONS

10.1 Study Hypotheses

We hypothesis that Dex4® tablets will provide an equivalent carbohydrate challenge for diagnosis gestational diabetes and result in fewer side effects than glucose beverage.

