2.1 Background

Gestational diabetes mellitus (GDM) is defined as any degree of hyperglycemia with onset or first recognition during pregnancy (5-6). Up to 70% of women with GDM will develop type 2 diabetes mellitus (T2DM) during their lifetime (3). Diabetes Canada and the Society of Obstetricians and Gynecologists of Canada recommend that pregnant women be screened for GDM between 24-28 weeks of pregnancy (7,8). The current 2-step approach for GDM detection involves a screening test and a diagnostic test, both of which use a liquid glucose challenge. In Canada, most pregnant women routinely undergo screening for GDM by consuming 50g of a liquid glucose solution and having a blood test for serum glucose after 1 hr, this test is commonly known as the 50g glucose challenge test (50g GCT). Women with a positive screening test (serum glucose 7.9 to 11.0 mmol/L) take a second test to confirm the diagnosis. For the second test, called a 2 hour oral glucose tolerance test (OGTT), women fast for 8 hours and then consume 75g of glucose beverage, and serum glucose levels are taken at fasting, 1 and 2 hours after drinking the glucose beverage. The 75g OGTT is the gold standard and is performed for GDM diagnosis.

Unfortunately, up to 30% of women do not tolerate glucose beverage (9-11). Side effects include: nausea, vomiting, bloating, abdominal pain, diarrhea, sweating and headache which may prevent them from completing testing for GDM (9-11). If women cannot complete screening, the diagnosis of GDM may be missed, increasing the risk of complications for mothers and their babies, such as a larger baby and trauma during delivery. Women who have had a history of GDM are at higher risk of developing cardiometabolic complications such as lipid abnormalities, hypertension and hyperinsulinemia (5, 15). GDM also carries a risk for later development of T2DM to the mother and fetus (2, 3). Unfortunately, GDM prevalence has doubled in the past 10 years in all ethnic populations and reaches 25-32% in some (16-19), with an estimated 19% of cases proceeding on to become T2DM within the first 9 years after pregnancy (2). Because of T2DM's long asymptomatic phase, many women will have already developed health complications by the time they are diagnosed. A missed diagnosis of GDM is a missed opportunity to intervene and offer prevention for T2DM.

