Other alternatives to the standard glucose beverage such as jelly beans and candy twists (Twizzlers) have been suggested in the literature but are limited by their diagnostic accuracy and portion size, respectively (13). However, Dex4® tablets may not have this issue. As Dex4® tablets are normally used to correct hypoglycemia in people living with diabetes, portion sizes

are manufactured to be more precise compared to most candies, and lots are regularly analyzed to confirm tablet size, hardness, and dextrose monohydrate content.

The purpose of this study is to compare the positive and negative effects of Dex4® tablets, as an alternative form of fast acting carbohydrate, compared to the current standard diagnostic test, glucose beverage. We hypothesize that because of their availability in solid, chewable form, variety of flavours and lack of carbonation, Dex4® tablets may result in fewer side effects than glucose beverage and provide an equivalent carbohydrate challenge for diagnosis gestational diabetes.

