3 STUDY OBJECTIVES

3.1 Primary Objective

Primary objective 1 (PO-1): to determine if Dex4® tablets is equivalent to glucose beverage for use in the 2-hr 75g OGTT in pregnant women between 24-32 weeks gestation who have screened positive for GDM.

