4.2 Primary Outcomes/Endpoint(s)

The primary outcome measures are fasting 1hr and 2hr PG levels from the Dex4® and glucose beverage OGTTs. Serum glucose values after a carbohydrate load have significant intra-individual variation, if done on the same person but at a different time the results can vary up to 16.7% (21) The two tests will be considered equivalent if the difference between them is less than or equal to 20%.

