4.3 Secondary Outcomes/Endpoint(s)

The secondary outcome measures are side effects associated with Dex4® tablets and participant preference of using Dex4® tablets or the standard glucose beverage for OGTT testing.

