5 PARTICIPANT SELECTION AND WITHDRAWAL

This is a study of diagnostic test validity in pregnant women, so this vulnerable population is the only population that can be studied. Women will be offered enrollment if they fall into the screen positive group after a 50g GCT. Only singleton pregnancies will be included as twin gestations can have higher glucose values and this may impact the generalizability of the results. Women can withdraw from the study at any time, but will be encouraged to complete the standard glucose beverage test as this is the only validated test to provide a diagnosis of GDM at this time. A sample of 28 will provide 80% power at alpha of 0.05 for a test of equivalence with Dex4® tablets assuming a 20% margin of equivalence. The sample size calculation was carried out using PASS Version 12 (Hintze, J. (2014). NCSS, LLC. Kaysville, Utah.) Accounting for loss to follow up of 33%, 42 women will need to be recruited, respectively. Based on data from Alberta, 20% of women screen positive on a 50g GCT (22). Approximately 230 women deliver at Sunnybrook every month, of those 45 will screen positive on the GCT. Assuming a 20% successful recruitment rate we should be able to complete recruitment in 4-6 months. Eligibility criteria must be met by 32 weeks' gestation to allow enrollment in the study.

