10.4 Final Analysis Plan

Serum glucose values after a carbohydrate load have significant intra-individual variation, if done on the same person but at a different time the results can vary up to 16.7% (21) The two tests will be considered equivalent if the difference between them is less than or equal to 20%. For a mean one hour post 75g carbohydrate load serum blood glucose of 10.6 mmol/L (standard deviation of 1.78 mmol/L) a sample of 28 will provide 80% power at alpha of 0.05 for a test of equivalence with Dex4® tablets assuming a 20% margin of equivalence. The sample size calculation was carried out using PASS Version 12 (Hintze, J. (2014). NCSS, LLC. Kaysville, Utah.) Accounting for loss to follow up of 33%, 42 women will need to be recruited, respectively.

To evaluate equivalence, the mean of the differences at each time point (fasting, 1 hr and 2 hrs after glucose beverage/Dex4® tablets) will be calculated and a two-sample equivalence-test will be used to compare the means. Based on previous reports of intra-individual variation in 2 hour OGTT of 16.7% for blood glucose measurement (21), Dex4® tablets will be considered equivalent to glucose beverage if the equivalence margin is less than or equal to 20%.

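### The hypothesis is equivalence for diagnosing GDM, but the outcomes and decision rule compare only mean glucose, side effects and preference, so meeting the rule cannot support a diagnostic claim

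*Protocol*

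**What the plan says.** The protocol frames its question diagnostically in several places. The hypothesis in 10.1 is that "Dex4® tablets will provide an equivalent carbohydrate challenge for diagnosis gestational diabetes". Section 5 states: "This is a study of diagnostic test validity in pregnant women". Section 2.1 describes earlier candy alternatives as "limited by their diagnostic accuracy and portion size, respectively". The formal primary objective (3.1) is "to determine if Dex4® tablets is equivalent to glucose beverage for use in the 2-hr 75g OGTT in pregnant women". It does not mention diagnosis, but 2.1 says of that test: "The 75g OGTT is the gold standard and is performed for GDM diagnosis".

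The measurements are narrower. Section 4.2: "The primary outcome measures are fasting 1hr and 2hr PG levels from the Dex4® and glucose beverage OGTTs". Section 10.4: "the mean of the differences at each time point (fasting, 1 hr and 2 hrs after glucose beverage/Dex4® tablets) will be calculated", followed by an equivalence test on the means with a 20% margin. Section 4.3: "The secondary outcome measures are side effects associated with Dex4® tablets and participant preference". The protocol states no cut-offs for the 75 g OGTT. It does not name classification, concordance, sensitivity, specificity or within-woman agreement as an outcome or an analysis.

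Under 4.1 every woman takes both tests and all results go to the research team, while only the beverage result is used for her diagnosis.

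**The concern.** A diagnostic test is used one woman at a time against cut-offs. A test on group means answers a different question, and the gap has two parts. First, a mean shift small enough to pass the 20% rule can move a sizeable share of women from one side of a cut-off to the other. Second, even with no mean shift, individual differences can cancel in the mean while individual classifications disagree.

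What is at stake is the conclusion. A trial run exactly as written could meet its rule and be reported as showing equivalence for GDM diagnosis, although its analysis never tested that. Diagnostic accuracy is also the property on which section 2.1 faults an earlier alternative, and this plan does not assess it for Dex4.

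**Working it through.** **Inputs from the protocol (10.2, 10.4).** 1 h mean 10.6 mmol/L, SD 1.78, margin 20%, N = 28, alpha 0.05, power 80%. Margin in units: 0.20 × 10.6 = 2.12 mmol/L.

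**Assumptions, not in the protocol.** A 1 h cut-off of 9.6, 10.6 or 11.6 mmol/L; a true Dex4 shift of -1.0 mmol/L (1.0/10.6 = 9.4%, under half the margin); normal values with the same SD on both products; within-woman correlation r from 0 to 0.7. The 1 h value is used because it is the only time point with a planning mean and SD.

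**1. The plan's own figure.** Two one-sided tests at 0.05 each, true difference 0, two independent groups: 2 × [1.78 × (1.645 + 1.282)/2.12]² = 12.1 per group. With the t distribution, 13 per group gives 80.8% power and 14 per group gives 84.5%. So 28 is reproduced, within 2, as the total of two independent groups. With 28 women each doing both tests, power at zero shift is about 99% or more. Whether 28 suits a crossover is a separate matter. Here it means that the mean test has ample room to pass despite a real shift.

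**2. Share above the 1 h cut-off.** Share = 1 − Φ((cut-off − mean)/1.78), with mean 10.6 for the beverage and 9.6 for Dex4.

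| Assumed cut-off | Beverage | Dex4 | Fall (points) |
|---|---|---|---|
| 9.6 | 71% | 50% | 21 |
| 10.6 | 50% | 29% | 21 |
| 11.6 | 29% | 13% | 16 |

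**3. Chance that the mean test still passes at that shift.** SD of the paired difference = 1.78 × √(2(1 − r)). The test passes if the 90% confidence interval lies within ±2.12. For r = 0.5, the SD is 1.78 and the half-width is 1.703 × 1.78/√28 = 0.57. The observed difference must therefore exceed about -1.55. With a standard error of 0.336, the chance is Φ((1.55 − 1.0)/0.336) ≈ 95%. Simulated results:

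| r | SD of difference | Paired test | Two-sample test on the same data |
|---|---|---|---|
| 0 | 2.52 | 74% | 75% |
| 0.3 | 2.11 | 86% | 79% |
| 0.5 | 1.78 | 94% | 83% |
| 0.7 | 1.38 | 99% | 88% |

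Section 10.4 mentions both the mean of the differences and a two-sample test. The result is similar under either reading.

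**4. No mean shift at all.** At a cut-off equal to the mean, the share of women classified differently at 1 h is arccos(r)/π: 33% at r = 0.5 and 14% at r = 0.9. At a cut-off of 9.6 or 11.6 the figures are 28% and 12%. A test on means does not register this.

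**5. What 28 women can say about agreement.** Exact 95% intervals: 28/28 gives 87.7–100%; 26/28 gives 76.5–99.1%; 11/14 (if half are positive) gives 49–95%.

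**The case against.** **The endpoint suits the hypothesis as worded.** The formal objective does not mention diagnosis, and what 10.1 calls equivalent is the carbohydrate challenge, to which serum glucose is the direct response. This stands in part. Mean glucose is a sensible primary outcome for a phase II trial of this size, and 3.1 and 4.2 do not contradict each other. It does not remove the diagnostic wording in 10.1 and section 5, which no outcome addresses.

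**A separate statistical analysis plan may add agreement tables.** It may, and none was available. But the protocol itself sets the hypothesis, the outcomes and the equivalence rule, and the mismatch lies among those.

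**The illustration is partly a complaint about the 20% margin.** This is fair for the shift argument. A narrower margin would shrink the first gap, but would leave the second untouched.

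**Stronger readings that the document does not support.**
- A reader might infer that Dex4 would miss or over-call a large share of GDM cases. This is not shown. The shares above concern one time point and assumed cut-offs. The OGTT has three time points, and the fasting sample is drawn before ingestion, so Dex4 cannot shift it.
- A reader might take a shift as large as the margin as typical of what would pass. At that shift the test passes only about 5% of the time.
- A reader might treat the 16.7% variation as a within-person coefficient of variation and derive individual limits from it. That gives a within-person SD of 0.167 × 10.6 = 1.77 against a total SD of 1.78, hence a correlation near 0. The protocol says only that results can vary up to that figure.
- Disagreement at zero shift is not evidence against Dex4, because repeating the beverage test would also produce some.
- No participant's diagnosis is at risk, because only the beverage result is used.

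**Conclusion.** The point holds as a mismatch between the claim and the analysis. The hypothesis and section 5 speak of diagnosis, while the outcomes and decision rule do not. That conclusion follows from the text alone and needs no assumed figure.

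Its possible size is illustrative. At a true shift of -1.0 mmol/L, the share above an assumed 1 h cut-off of 9.6–11.6 falls by about 16 to 21 points, while the mean-equivalence test passes about 75% to 99% of the time for r between 0 and 0.7. Test-retest variation does not explain a net fall of that kind, although it would explain some of the individual disagreement. The protocol gives neither the OGTT cut-offs nor the within-woman correlation, so no GDM misclassification rate can be derived from it.

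The trial can run as designed. What should change before analysis is the set of secondary outcomes and the reach of the conclusion.

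**What to change.** 1. Add to 4.3 and 10.4 a descriptive secondary outcome. Classify each woman as GDM yes or no from each OGTT by the institution's cut-offs, prespecified in the protocol. Report the paired 2×2 table, positive and negative agreement with the beverage OGTT with exact 95% confidence intervals, and the number and direction of discordant pairs. Report 95% limits of agreement for the 1 h and 2 h differences. Read all of these against the test-retest variation expected of the beverage OGTT, with its source stated.

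2. State in 10.1 and 10.4 that meeting the mean-equivalence rule supports only an equivalent mean glucose response, and that this 28-woman trial will not by itself support a claim of equivalence for GDM diagnosis.

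The change costs protocol wording and an additional table. It needs no new visit, sample or participant. The downside is imprecision: agreement in 26 of 28 women would carry an interval of 76.5–99.1%, so the published conclusion becomes more cautious. Prespecifying the cut-offs also removes the scope for choosing them after the results are seen.
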